7.3. Subject Withdrawal/Discontinuation Criteria

Subjects may request to be withdrawn from the study at any time for any reason.

The Investigator may interrupt the treatment of any subject whose health or well-being may be compromised by continuation in the study. The following instances require subjects to be withdrawn from the study:

- Subject fails to adequately comply with the dosing, evaluations, or other requirements of the study at the discretion of Investigator.
- Subjects who have adverse events that require discontinuation of study medication;

- Subjects who, in the opinion of the Investigator, should be discontinued for their wellbeing;
- Subjects who start Esbriet® (Pirfenidone) or OFEVTM (Nintedanib) during the study.
- Subjects who are no longer able to understand task instructions or to perform tests adequately.
- Subject becomes pregnant during the study. See section 12.7 for reporting requirements and follow-up of the pregnancy.

If a subject withdraws or is removed from the study for any reason, the reason and date of discontinuation of study medication should be recorded in the appropriate section of the Case Report Form (CRF). At the time of study discontinuation, every effort should be made to ensure all Early Termination (ET) procedures and evaluations are performed.

The study sponsor reserve the right to discontinue the study at any time for medical or administrative reasons.

7.3.1. Individual Stopping Criteria

Subjects who experience an adverse event of Grade 2 nausea and/or diarrhea for greater than 3 consecutive days, or Grade 3 nausea and/or vomiting for greater than 1 day thought to be related to study drug will be discontinued from the study. Additionally, subjects who experience an adverse event of Grade 3 abdominal pain lasting for greater than 1 day thought to be related to study drug will be discontinued from the study.

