During the Screening Phase, subjects will be assessed for study eligibility. The following assessments will be performed: medical history including review of prior medications, physical examination including height and body weight, vital signs and an electrocardiogram. Clinical labs, chemistry (including liver enzymes and fasting lipid profile), hematology, urinalysis and a serum pregnancy test will be collected as well as serum lysyl oxidase-like 2 levels (LOXL2), a biomarker for IPF.

Double-blind Treatment Phase (26 weeks)

Subjects who complete all of the screening assessments and meet all inclusion/exclusion criteria will be started on MN-001 1500 mg to be administered as 750 mg bid or 500 mg tid, or matching placebo. Subjects will return to the clinic on Treatment Day 1 to receive their first dose of study medication. Subsequently, subjects will return to the clinic on a regular basis (see Table 1 Schedule of Assessments) for 26 weeks. Subjects participating in the study will return to the clinic Month 1 and every 3 months for evaluation. During the Treatment Phase, safety and efficacy parameters will be assessed and concomitant medications will be documented. The safety and tolerability of MN-001 will be evaluated by an Independent Safety Monitor during this phase.

Open-Label Extension (OLE) Phase (26 weeks)

Upon completion of the Double-blind Treatment Phase, subjects who were taking placebo, will participate in the open-label extension (OLE) phase for an additional 6 months. Subjects who were in the placebo group will be administered MN-001 750 mg bid or 500 mg tid for the remainder of the OLE Phase.

Subjects randomized to the MN-001 group will continue the study drug for additional 6 months. All subjects will return to the clinic for evaluation at 1 month and every 3 months after the start of the open-label extension phase (Months 7, 9 and 12).

Individual Stopping Criteria

Subjects who experience an adverse event of Grade 2 nausea and/or diarrhea for greater than 3 consecutive days or Grade 3 nausea and/or vomiting for greater than 1 day thought to be related to study drug will be discontinued from the study. Additionally, subjects who experience an adverse event of Grade 3 abdominal pain lasting for greater than 1 day thought to be related to study drug will be discontinued from the study.

Study Stopping Rules

The study will be stopped if two subjects experience a Grade 4 adverse event thought to be related to study drug.

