12.2.1. Severity Assessment

The severity of AEs will be determined as described in Table 7.

Table 7: Adverse Events Severity Definition

Mild Grade 1	Ordinarily transient symptoms that do not influence performance of subject's daily activities. Treatment is not ordinarily indicated.
Moderate Grade 2	Marked symptoms sufficient to make the subject uncomfortable. Moderate influence on performance of subject's daily activities. Treatment may be necessary.
Severe Grade 3	Symptoms cause considerable discomfort. Substantial influence on subject's daily activities. May be unable to continue in the study and treatment may be necessary.
Life- threatening Grade 4	Extreme limitation in activity, significant assistance required; significant medical/therapy intervention required hospitalization probable.
Death Grade 5	Death.

When changes in the intensity of an AE occur more frequently than once a day, the maximum intensity for the event should be noted for that day. Any change in severity of signs and symptoms over a number of days will be captured by recording a new AE, with the amended severity grade and the date (and time, if known) of the change.

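### The individual stopping criteria set a Grade 3 limit of more than 1 day for nausea, vomiting and abdominal pain, but not for diarrhea

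*Protocol*

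**What the plan says.** Protocol 7.3.1 lists three triggers for taking an individual subject out of the study. Two are in one sentence: "Grade 2 nausea and/or diarrhea for greater than 3 consecutive days, or Grade 3 nausea and/or vomiting for greater than 1 day". The third is a separate sentence for "Grade 3 abdominal pain lasting for greater than 1 day thought to be related to study drug will be discontinued". The synopsis states the same rule, differing in this clause only by the absence of a comma: "Grade 2 nausea and/or diarrhea for greater than 3 consecutive days or Grade 3 nausea and/or vomiting for greater than 1 day".

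Other provisions bear on the same event:

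- Section 7.3 requires withdrawal of "Subjects who have adverse events that require discontinuation of study medication" and of subjects who, "in the opinion of the Investigator, should be discontinued for their wellbeing". It also permits a pause in dosing: "The Investigator may interrupt the treatment of any subject whose health or well-being may be compromised by continuation in the study".
- Table 7 in 12.2.1 says of a Grade 3 event: "May be unable to continue in the study and treatment may be necessary".
- Section 6.3 has an independent safety monitor reviewing data in both treatment phases.
- The study-level rule in 7.3.2 concerns two subjects with related Grade 4 events, so it does not reach Grade 3.

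None of these gives a grade and duration limit for diarrhea, and neither document explains why diarrhea is left out at Grade 3.

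**The concern.** Nausea is the closest comparator because it shares the Grade 2 limb with diarrhea. When nausea goes from Grade 2 to Grade 3, its limit shortens from more than 3 days to more than 1 day. When diarrhea does the same, nothing shortens. Two subjects with drug-related gastrointestinal toxicity of the same grade and length can therefore be handled differently by the rule.

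The omitted event is also the gastrointestinal event that protocol 4.2.1 reports most prominently for this drug. In CL-001, of diarrhea, nausea and vomiting, only diarrhea was above 5% of MN-001 subjects. In CL-002 it was the commonest treatment-emergent event on MN-001. In the Phase 3 asthma study it occurred in 11 subjects (21%) on 750 mg bid and 5 (9%) on 500 mg tid, which are the two regimens allowed here. Prior dosing ran for up to 12 weeks; this trial doses for about 52.

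At stake is consistent handling of a tolerability event. The omission itself changes no efficacy analysis.

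**Working it through.** The plan attaches no figure to this rule, so there is none to reproduce. The check is to apply the criteria to short courses of related symptoms. Two readings of the Grade 2 limb are possible:

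- **Minimum reading:** Grade 2 or worse, with days counted over the continuous episode.
- **Strict reading:** exactly Grade 2.

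| Course | Diarrhea, minimum reading | Diarrhea, strict reading | Same course of nausea |
|---|---|---|---|
| A. 2 days Grade 3 | 2 days is not more than 3: no trigger | no trigger | 2 > 1 at Grade 3: stop |
| B. 1 day Grade 2, then 2 days Grade 3 | 1 + 2 = 3, not more than 3: no trigger | no trigger | stop |
| C. 2 days Grade 2, then 2 days Grade 3 | 2 + 2 = 4 > 3: stop | 2 days at Grade 2: no trigger | stop |
| D. 4 days Grade 3 | 4 > 3: stop | no trigger | stop |

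Courses A and B are missed on both readings. They define the secure gap: more than 1 day of related Grade 3 diarrhea inside an episode of 3 days or less at Grade 2 or worse. Courses C and D are missed only on the strict reading.

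The text does not settle which reading applies. Against the strict one, it would also leave Grade 4 nausea, vomiting and abdominal pain without an individual trigger, which is hard to believe was intended. In its favor, the limb does not say or worse, and 12.2.1 splits an episode when its grade changes: "Any change in severity of signs and symptoms over a number of days will be captured by recording a new AE". If the day count restarted with each new record, course C would be missed on the minimum reading too.

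How many subjects could be affected cannot be computed, because no Grade 3 diarrhea rate is given. For orientation only, assume that the Phase 3 all-grade rates carry over to the roughly 10 subjects on MN-001 (15 × 2/3):

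- Expected number with any diarrhea: 10 × 0.09 = 0.9 to 10 × 0.21 = 2.1.
- Probability of at least one: 1 − 0.91^10 = 0.61 to 1 − 0.79^10 = 0.91.

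These figures say that diarrhea of some grade is likely to be seen. They say nothing about short Grade 3 episodes, which are a subset of unknown and probably small size.

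**The case against.** The strongest reply is that protection already exists. Under 7.3, once the Investigator judges that an adverse event requires stopping drug, or that the subject should stop for their wellbeing, withdrawal is mandatory. The 7.3.1 triggers rest on judgment too, since grade and relatedness are Investigator assessments. A reader might infer from 7.3.1 that subjects with Grade 3 diarrhea are unprotected; the documents do not support that. What stands against the reply is that the same general provisions cover nausea, vomiting and abdominal pain, and the sponsor still wrote explicit limits for those three.

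A second reply is that the limits already differ by event: vomiting and abdominal pain have no Grade 2 trigger. That is true, and asymmetry alone is not a defect. The case rests on the narrower comparison with nausea, and on diarrhea being the prominent event for this drug.

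A third is that the prior data are compatible with tolerating brief diarrhea. The Phase 1 single-dose summary describes it as mild, CL-001 had no severe gastrointestinal events and none that led to discontinuation, and 4.1.1 describes 1500 mg/day as tolerated over 12 weeks. This also stands. The rates cited are frequencies, and a reader should not take them as evidence that severe diarrhea is common.

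**Conclusion.** The omission is real, present in both places and unexplained. It is minor. The secure gap is related Grade 3 diarrhea of more than 1 day within an episode of 3 days or less at Grade 2 or worse. This rests on reading Grade 2 as a minimum and counting days across the episode.

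Two stronger statements are tempting. One is that Grade 3 diarrhea of any length escapes; that follows only from the strict reading, which the text does not establish. The other is to size the gap as extra drug taken before a trigger is reached. Such a figure fits only episodes that run past 3 days, which do trigger on the minimum reading, and it assumes full dosing throughout although 7.3 permits interruption. For an episode inside the gap, no trigger ever comes, and the contrast is between leaving the study and staying in it. No dose figure and no probability should be attached. The case is probably rare.

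**What to change.** In 7.3.1 and in the synopsis, change only the Grade 3 nausea and vomiting limb so that it names *nausea, vomiting and/or diarrhea*, keeping its more-than-1-day limit and its relatedness condition. All four courses in the table then trigger for diarrhea on either reading.

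Leave the Grade 2 limb as it is. The comma in 7.3.1 may mean that its trigger does not depend on relatedness. A rewrite that applied relatedness to the whole sentence could loosen an existing safety rule.

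The cost is a short amendment with written Sponsor and IRB approval (17.1) and an occasional extra discontinuation. One subject is 1/15 = 6.7% of the planned sample and, if on MN-001, about 1/10 = 10% of that arm. Because the rule removes the subject from the study, possibly after the event has resolved, later FVC data may be lost.

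The SAP, dated April 2021, describes randomization in the past tense (SAP 6.3). If dosing has ended, put the wording into the next MN-001 protocol.

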7.3.2. Study Stopping Rules

The study will be stopped if two subjects experience any Grade 4 (i.e., life-threatening consequences; urgent intervention indicated) adverse event thought to be related to study drug. The medical monitor will review the cases with the PI prior to the decision to terminate the study is made.

7.3.3. Follow-up Procedures Upon Discontinuation/Withdrawal

A termination CRF page should be completed for every subject who received study medication whether or not the subject completed the study. The reason for discontinuation should be indicated on the CRF. Any AEs that are present at the time of discontinuation/ withdrawal should be followed in accordance with the safety requirements outlined in Section 12.

8. TREATMENT OF SUBJECTS

8.1. Description of Study Drug

MN-001 250 mg tablets will be provided in bottles and will be stored at room temperature.

8.2. Concomitant Medications

Concomitant medications required for the treatment of symptoms and signs of idiopathic pulmonary fibrosis are permitted except as excluded below.

Patients who are treated with OFEVTM (Nintedanib) should be on a stable dose for at least 3 months prior to study drug treatment.

Concomitant medications for treatment of adverse events may be allowed. Subjects will be instructed to contact a member of the study staff prior to taking any medication.

8.3. Prohibited Medications

The following medications are **prohibited** prior to and during study participation:

- Ongoing IPF treatments with investigational therapy
- Ongoing IPF treatment with Esbriet® (Pirfenidone)
- Immunosuppressants (i.e., Mycophenolate, Imuran, Cyclophosphamide), and cytokine modulating agents within 1 month of Screening Visit and throughout the study
- CYP2C8 and CYP2C9 substrates with narrow therapeutic indices (i.e. paclitaxel, phenytoin and S-warfarin) within 14 days of Screening Visit and throughout the study.
- Macrolides and other antibiotics within 14 days of Screening Visit and throughout the study unless administered for a short-term treatment course during the study.
- Antibiotics and systemic steroids due to IPF exacerbation within 1 month of screening visit.

The medical monitor should be consulted prior to administration of a prohibited concomitant medication.

8.4. Treatment Compliance

Compliance will be monitored closely at each visit. Subjects will be instructed to bring all unused study medication with them to each visit. Compliance will be assessed by counting capsules and dividing the actual number of doses taken (per capsule count) by the number of doses the subject should have taken within a visit period and multiplying by 100. All subjects will be reminded of the importance of strict compliance with taking study medication for the effectiveness of treatment and for the successful outcome of the study. Subjects who miss more than 25% of scheduled doses or take more than 125% of the scheduled doses will be considered noncompliant and may be discontinued from the study per investigator's judgment.

8.5. Randomization and Blinding

During the Double-Blind Treatment Phase, randomization will occur in a 2:1 ratio (MN-001: placebo). The randomization scheme will be generated by the research software application, StudyTRAX. Subjects and all personnel involved with the conduct and interpretation of the study, including the investigators, site personnel, and sponsor staff will be blinded to the treatment codes. Randomization data will be kept strictly confidential, filed securely by an appropriate group with the sponsor and accessible only to authorized persons (e.g., unblinded independent safety monitor) until the database is locked.

To ensure that treatment allocation remains concealed to both staff and participants, the following measures will be taken:

- Active drug and placebo will be identical in appearance
- Drug supplies to investigational pharmacy will be coded

8.5.1. Emergency Unblinding Procedure

A master list of all treatments and the subject numbers associated with them will be maintained in a sealed envelope by the sponsor. In the event that emergency conditions require knowledge of the study treatment given, the blind may be broken. If possible, before breaking the blind, the investigator should consult with the sponsor to ascertain the necessity of breaking the code.

Unblinding may take place in situations where the safe management of the patient's medical condition necessitates knowledge of the study medication by the person(s) responsible for the patient's care. Where possible, members of the local research team should remain unblinded.

If unblinding is required, the local PI/other medical staff should contact the sponsor at [contact]- via telephone or [contact] via email.

The person requesting the unblinding will provide details including the protocol number and trial name, name of the requester, reason for unblinding, patient name, participant number and timeline to receive the un-blinded information. If knowledge of the treatment allocation is required in order to treat the patient, the code break number will be given to the local PI/other medical staff requesting to unblind the patient. In this way, the treatment will be un-blinded at the local site but not to sponsor.

The local PI/medical staff will deal with the medical emergency (upon receipt of the treatment allocation revealed by the code break number). Details of the code break will be documented on the code break form and filed at the local site.

Code breaks will also be documented at the end of the study in the statistical report.

8.6. Dosing Guidelines

8.6.1. Treatment Phase

On Day 1, once baseline assessments are completed, subjects will be administered their first dose of study drug (MN-001 or matching placebo) in the clinic. Subjects will continue to take study drug twice or 3 times daily for 26 weeks during the Double-blind phase. Upon completion of the

Double-blind Treatment Phase, subjects who were taking placebo will participate in the open-label extension (OLE) phase for 26 weeks. Subjects who were taking MN-001 will continue to take MN-001 for 26 weeks.

8.7. Written Informed Consent

Each subject is required to provide written informed consent prior to undergoing any study procedures. A copy of the signed and dated informed consent form (in a language in which the subject is fluent) is required to be given to the subject. If a subject withdraws consent, data collected up to the time of discontinuation will be used to evaluate study results.

8.8. Assessments

The Schedule of Assessments is presented in Table 1.

Clinical laboratory evaluations will be performed. All clinical and laboratory evaluations, procedures related to inclusion/exclusion criteria, or performed during treatment must be reviewed, initialed and dated by the Principal Investigator or appropriate designee listed on Form FDA 1572.

8.8.1. Study Assessments by Visit

The following is a summary of assessments by study visit.

8.8.1.1. Screening Phase (Up to 3 months prior to Day 1)

Visit 1 (Day -90 to Day -8)

At any point during this time, subject may be approached for participation in the study. An informed consent form (ICF) will be given to the subject and the subject will be instructed to read the ICF and ask the study staff any questions they may have. The subject can either sign the ICF then or defer signing until they return for Study Visit 2.

Visit 2 (Day- 7 ± 5 days)

During the Screening Phase, once the informed consent form is signed, the following assessments will be performed/collected):

- Inclusion/Exclusion criteria review
- Medical history
- Physical examination
- Height/body weight
- Vital signs including supine blood pressure, respiratory rate, heart rate, and temperature
- 12 lead Electrocardiogram (ECG)
- Fasting safety labs chemistry (including CPK, liver enzymes, lipid panel) hematology, and urinalysis labs

- Serum β-hCG (pre-menopausal females)
- Blood Sample for biomarker
- Prior/concomitant medication review
- Pulmonary function test
- 6 minute-walk test (6MWT)*
- Dyspnea score (MMRC: Modified Medical Research Council Dyspnea Score)
- ATAQ-IPF (A Tool to Assess Quality of Life in IPF)

The results of pulmonary function test, 6MWT, MMRC and ATAQ-IPF at this visit are considered "Baseline" values.

* Two tests should be performed for 6MWT

8.8.1.2. Double-Blind Treatment Phase (26 weeks)

Subjects will enter the clinic in the morning prior to breakfast. Once the pre-dose fasting labs have been completed, subjects will be given breakfast except on Baseline Day 1.

Baseline Clinic Visit: Day 1

The following assessment will be done:

- Inclusion/Exclusion criteria review
- Vital signs including supine blood pressure, respiratory rate, heart rate, and temperature
- Urine β-hCG (in pre-menopausal females)
- Concomitant medication review
- Adverse event review
- Dispense study drug
- Dispense patient diary
- 12-lead ECG at Hour 1.5 (\pm 30 minutes) post dose

Once the pre-dose assessments have been completed, the subject will be administered the first dose of MN-001 (2 or 3 tablets of MN-001 250 mg) or matching placebo with water.

Clinic Visits: Months 1, 3 and 6* (± 5 days)

The following assessments will be done:

- Physical examination
- Body weight
- Vital signs including supine blood pressure, respiratory rate, heart rate, and temperature
- 12-lead ECG at Hour 1.5 (± 30 min) post dose

- Fasting safety labs chemistry (including CPK, liver enzymes, lipid panel) hematology, and urinalysis labs
- Urine β-hCG (pre-menopausal females)
- Blood Sample for biomarker (Month 6 only)
- Pulmonary function test (Months 3 and 6 only)
- 6MWT (Months 3 and 6 only)**
- Dyspnea score (MMRC)
- ATAQ-IPF (Months 3 and 6 only)
- Adverse event review
- Concomitant medication review
- Patient diary review
- Dispense study drug (Months 3 and 6 only)
- Study drug accountability
 - * Month 6 Clinic Visit is the start day (Day 1) of the Open-Label Extension (OLE) phase. All subjects will take MN-001 750 mg bid or 500 mg tid.
 - ** Two tests should be performed for 6MWT

Telephone Visits Week 1 (\pm 3 days) and Month 4 (\pm 5 days)

Between clinic visits, subjects will be called by a study team member (e.g., study coordinator or nurse) to collect information regarding their health status. The MMRC will be administered (only Month 4) and adverse events and concomitant medications will be documented.

